#### Additional Outcomes:

- a. Acute care utilization: Median length of stay (LOS) in hours, all-cause Emergency Room (ER) visit, and hospital readmission within 30 days postoperatively
- b. Implementation and feasibility outcomes: We will also perform psychometric assessments, from the perspective of patient and nursing stakeholders, of the implementation process and perceived effectiveness associated with our passive vital sign monitoring intervention. Three 5-item validated implementation metrics of Acceptability (AIM), Appropriateness (IAM), Feasibility (FIM) will be used to monitor and evaluate the adoption of our passive vital signs monitoring intervention. We will also leverage the system usability scale (SUS) to examine the usability and ergonomics of the passive vital sign monitoring platform (Table 3).

Outcome	Instrument	Duration	Analysis level	Assessment Calendar
Intervention	System Usability Scale	5 mins	Patient, Nurse	Admit, discharge +/- 1
usability				day
Intervention	Acceptability of Intervention	3 min	Patient, Nurse	Admit, discharge +/- 1
acceptance	measure (AIM)			day
Intervention	Feasibility of Intervention	2-5 min	Patient, Nurse	Admit, discharge +/- 1
feasibility	Measure (FIM)			day
Intervention	Intervention Appropriateness	2-5 min	Provider,	Admit, discharge +/- 1
appropriateness	Measure (IAM)		Nurse	day

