#### 1.2 Secondary Objectives:

- a. Assess the impact of our sleep enhancement intervention on acute care utilization e.g. length of stay, 30-day readmissions
- b. Assess the implementation and feasibility of wearable digital vital signs capture in an inpatient oncologic setting using validated instruments such as system usability scale (SUS) and Weiner implementation outcomes (AIM, FIM, IAM).
- c. Assess the impact, via validated survey instruments, of our sleep enhancement intervention on patient mood, patient activation and satisfaction with inpatient stay experience.

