#### 2.0 Background/Rationale

Post hospitalization syndrome refers to a generalized increased risk for a range of adverse health related events following an acute hospitalization. The mechanism is thought to be driven by allostatic and physiologic stress acquired during the hospitalization. Sleep disruptions, deconditioning from acute illness, loss of personal autonomy, pain, and disruption of normal circadian rhythms are prominent examples. Numerous reports have documented the prevalence and risk of these perturbations. The clinical impact of post-hospitalization syndrome is also being increasingly recognized. This includes but is not limited to immune dysfunction, coagulopathy, impaired physical coordination and poor wound healing. According to estimates, up to 20% of Medicare beneficiaries (approx. 2.6 million seniors) are readmitted within 30 days for reasons unrelated to the diagnosis that prompted the index admission. As a result, post-hospitalization syndrome has become the impetus for numerous quality improvement (QI) initiatives that promote successful recovery. A prominent example involves a multi-level QI project implemented at Ochsner clinic that bundled reduced nighttime noise, passive vital monitoring, delayed morning phlebotomy and use of red-enriched lighting after sunset. This program was associated with reduced length of stay (LOS), improved readmission rates and enhanced sleep quality across a sample of 3425 consecutive medical-surgical patients. However, it is unclear whether and to what extent these findings are generalizable to a population of acute care cancer patients. Phase I of the PROSPER protocol involved the use of various standard of care methods to minimize sleep interruptions during the hours or 10pm to 6am including, noise monitoring and reduction strategies, minimizing bedtime medication administration, delayed early morning phlebotomy, and use of red-light instead of white light when provider-patient interactions were necessary. These interventions were bundled into a "clustered care approach" along with eliminating nocturnal vital sign check when possible. Clustered care has been shown to improve sleep quality, improve

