#### **Hypothesis**

We hypothesize that the implementation of our wearable technology intervention will result in a reduced LOS, lower 30-day readmission rates, and improved patient recovery (sleep quality and quantity), and enhanced subjective measures of patient engagement (PAM-13), satisfaction (HCAHPS) and well-being (EQ-5D-5L).

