#### 3.0 Research Plan

#### 3.1 Study Population

This study will include consented consecutive patients who are admitted to the medical-surgical floor at MD Anderson Cancer Center (Texas Medical Center location only) for the conditions and/or surgical procedures outlined below.

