#### Table 1: Study participants

Participating Surgical Services	Participating Medical Services
Colorectal Surgery	Hospitalist service

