#### 3.4 Study Design

This is a pragmatic, quasi-experimental study wherein patients admitted for any of the aforementioned conditions will be allocated into treatment (ViSi mobile plus PROSPER) and control (PROSPER only) based on non-critical care bed availability on a floor unit. Specifically, for patients on colorectal service admitted to P10 floor, one side ("unit A") will be designated as an intervention arm while the other ("unit B") will serve as a control arm. For patients admitted to Hospitalist Medicine service; patients on " unit G21" will be designated as the intervention arm, and patients admitted to "unit G22" as the control arm. Our pseudorandomization scheme is based on the naturally occurring random variation in bed assignment by availability across both the intervention and control units on a given floor, or floors at the time of patient enrollment. Since bed designation is made by hospital admissions based on availability, it is independent of the care delivery processes across the study floors / units. Our approach is intended to reduce the

burden on frontline staff, i.e., changing existing workflows to randomize patients and track allocation in a database. It also serves to reinforce the embedded intent of our QI work. Participants, family members and clinicians will not be blinded to the intervention, and given our pragmatic design, we will not attempt to control patients' communication or information-seeking behaviors beyond the pseudo-randomization described above. The intervention wing will employ the following initiatives to improve the sleep quality, level of engagement, and overall care journey of patients.

1. Passive digital monitoring of vital signs – Blood pressure, heart rate, respiratory rate, oxygen saturation, and temperature – will be wirelessly and passively collected using a U.S. Food and Drug Administration-approved wireless technology, which is worn on the wrist and chest (ViSiMobile, Sotera, San Diego, Calif), and recorded data will be sent directly to the electronic medical record (Epic Systems Corporation, Verona,Wis) at protocolized set intervals. Abnormal vitals will trigger a nursing alert via text message or page. If an in-person assessment is warranted, handheld red-spectrum lighting will be used by nursing staff as an alternative to the standard overhead white lighting.

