#### 3.8 Data collection

This will entail a blend of Epic medical record abstraction and primary data collection using validated surveys. Example of variables to be exstracted from the medical record include patient demographics (e.g., age, sex, race), primary diagnosis (cancer type), body mass index (BMI), timing of AM phlebotomy, comorbid conditions (used to compute Charlson co-morbidity index), length of stay, and 30-day readmission. To reduce survey burden for patients and ensure parity in scope of responses across the 2 groups, the majority of questionnaires will be distributed at two time points - at admission and within 24 hours of the date of discharge. All validated surveys will be administered via the hospital-owned iPad device, via text message or email, or recorded manually. A password-protected database will be used to collate the clinical and outcomes data collected. Lastly, all patients will receive a phone call 24 hours after discharge to ensure all questions are answered and follow-up care has been arranged.

2022-0190 v.23Mar2023 Page **4** of **18** 

The digital device is worn on the wrist, like a watch, and provides continuous vital sign monitoring using a three-lead system that included electrocardiography (ECG), pulse oximetry, continuous noninvasive blood pressure, mean arterial pressure, temperature, respiratory rate, heart rate, and pulse rate. Patients will be able to view their vital signs on the wrist-worn device's display screen.

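### The 30-day readmission window is given a start point only by reference to surgery, which unoperated Hospitalist patients, enrolled in both arms, do not have

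*Combined protocol and SAP*

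**What the plan says.** Section 3.9, Additional Outcomes, item a, lists median length of stay, all-cause ER visit and "hospital readmission within 30 days postoperatively".

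The other places that mention the trial's readmission outcome give a length but no start:
- Section 1.2, item a: "acute care utilization e.g. length of stay, 30-day readmissions".
- Hypothesis: the intervention "will result in a reduced LOS, lower 30-day readmission rates".
- Section 3.8, among the variables taken from the medical record: "length of stay, and 30-day readmission".

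The Background (2.0) speaks of Medicare beneficiaries "readmitted within 30 days for reasons unrelated to the diagnosis that prompted the index admission". This is context for the study and not a definition of its outcome.

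On who is enrolled, section 3.1 takes patients admitted "for the conditions and/or surgical procedures outlined below". Table 1 names Colorectal Surgery as the surgical service and "Hospitalist service" as the medical one. Section 3.4 allocates the medical patients by unit: "For patients admitted to Hospitalist Medicine service", G21 is the intervention arm and G22 the control arm. The inclusion criteria in 3.2 ask for at least three nights in hospital and do not mention an operation.

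Section 3.10 assigns care utilization outcomes to time-to-event models and log-rank tests, states no time zero, and places all analyses in an intent-to-treat framework.

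**The concern.** A window counted from surgery can be applied only to patients who had surgery. A Hospitalist patient treated medically has no such date, and the same is true of any Colorectal patient admitted without an operation. A time-to-event analysis needs an origin for every patient, so the rule as written returns no value for part of the population that intent-to-treat requires to be analysed.

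The gap would have to be closed after the data exist: by leaving patients out, by choosing another start date, or by using different dates for the two services. The study is unblinded and not formally randomized, so such choices are better fixed in advance. Lower readmission is one of the plan's stated expectations, so this is not an incidental variable.

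The sentence in 3.9 can also be read in two ways for the ER visit. Either the 30-day postoperative limit covers it too, or the ER visit has no window at all.

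A smaller matter concerns operated patients. A fixed postoperative window leaves fewer post-discharge days at risk when the stay is longer, and the intervention is hypothesized to shorten the stay.

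**Working it through.** **1. Start points, side by side.** The plan gives no figure to reproduce here, so the check is of the text.

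| Section | Length | Start point |
|---|---|---|
| 1.2 a | 30 days | none |
| Hypothesis | 30 days | none |
| 3.8 | 30 days | none |
| 3.9 a | 30 days | operation |
| 3.10 | not stated | none |

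The only stated origin is the operation. Sections 3.1, 3.2, 3.4 and Table 1 together admit unoperated patients to both arms. The outcome is therefore undefined for them. The missing-at-random assumption in 3.10 does not help, because an undefined outcome is not a missing one.

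**2. How many patients.** The planned total is 2 × 350 = 700 (section 3.11). The documents give neither the split by service nor the number who will be operated on. With an assumed unoperated share s, the number without a window is 700s. If those patients were excluded equally from both arms, the unweighted standard error (SE) of the readmission difference would be multiplied by 1/√(1 − s).

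| Assumed s | No window | SE multiplier | Left per arm |
|---|---|---|---|
| 0.25 | 175 | 1.15 | 262.5 |
| 0.50 | 350 | 1.41 | 175 |
| 0.75 | 525 | 2.00 | 87.5 |

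For example, at an assumed 20% readmission rate, SE = √(2 × 0.2 × 0.8/n). This is 3.02 percentage points at n = 350 per arm, and 3.49, 4.28 and 6.05 points at the three reduced sizes. Propensity weighting and the unit random intercept are ignored.

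**3. Days at risk in operated patients.** If surgery is on the day of admission (an assumption), stays of 3, 5, 7 and 10 days leave 27, 25, 23 and 20 post-discharge days inside the window.

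Assume a constant post-discharge hazard h = −ln(1 − r)/30, where r is the readmission rate over 30 days after discharge. The counted proportion is 1 − exp(−h(30 − stay)). I take r = 10% and 20%; the Background's upper figure of 20% is for Medicare beneficiaries, not this population.

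| Stay, days | r = 10% (h = 0.003512) | r = 20% (h = 0.007438) |
|---|---|---|
| 5 vs 4 | 8.41% vs 8.73% (+0.32) | 16.97% vs 17.58% (+0.62) |
| 7 vs 6 | 7.76% vs 8.08% (+0.32) | 15.72% vs 16.35% (+0.62) |
| 10 vs 9 | 6.78% vs 7.11% (+0.33) | 13.82% vs 14.46% (+0.64) |

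The arm discharged one day earlier thus counts 0.32 to 0.64 points more readmissions. Relative to the unweighted SE of the difference, the shift per day of stay depends on who is analysed:
- All patients operated, 350 per arm: SE 1.92 to 2.86 points, shift 0.15 to 0.24 SE.
- Half operated, the rest counted for 30 days from discharge, 350 per arm: shift 0.16 to 0.32 points, about 0.07 to 0.11 SE.
- Half operated, the rest excluded, 175 per arm: shift 0.32 to 0.64 points, about 0.11 to 0.17 SE.

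If patients enter the risk set only at discharge and the hazard is constant, the shift is zero.

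**The case against.** The strongest reply is that the plan turns on one loosely chosen adverb. Readmission presupposes a discharge, the Background frames it against an index admission, and section 3.8 extracts it for all patients without distinguishing services. On that reading any analyst would count from discharge. This is plausible and may be what was meant. It does not settle the matter, because the trial does enrol a surgical service, for which a postoperative window is a reasonable literal rule. The text does not show whether the phrase is a slip, a rule for Colorectal patients, or a rule for everyone.

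Two stronger inferences are tempting, and neither is supported:
- A reader might infer that the Hospitalist patients will be lost from the readmission analysis. The documents do not say so, and the intent-to-treat statement in 3.10 points the other way. The standard-error multipliers describe a worst case on an assumed split; they are not an expected effect.
- A reader might infer that the readmission comparison is biased through length of stay. That needs a real effect on stay, and readmission either counted as a proportion or timed from surgery without delayed entry. Even then the tilt is a fraction of one standard error per day and works against the hypothesized benefit.

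It is also fair to say that a prespecified origin for each service would close the gap. Index discharge is the simpler choice because every patient discharged alive has that date. It does take in-hospital deaths out of the risk set, so the plan must say how they are reported.

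**Conclusion.** The concern holds as a defect in the definition of a secondary outcome. The one start point the plan supplies cannot be applied to unoperated patients, who are eligible in both arms and must be analysed, and section 3.10 supplies no substitute. Whether the ER visit shares the window is also unresolved.

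The size cannot be fixed from the documents. The counts of 175 to 525 and the multipliers of 1.15 to 2.00 rest on assumed shares of 25% to 75%, and the multipliers also rest on exclusion. The length-of-stay tilt rests on a constant hazard and assumed rates of 10% to 20%; it is secondary, and the point does not depend on it.

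Nothing here reaches the primary EQ-5D comparison or the sample size, and a reader should not infer that it does. The correction should be made before analysis, but it is not a threat to the trial's main result.

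**What to change.** - **Section 3.9, item a:** define all-cause ER visit and hospital readmission, for both services, as occurring within 30 days after discharge from the index admission. This also settles whether the window covers the ER visit.
- **Section 3.10:** start the time-to-event clock for these two outcomes at index discharge. State that patients who die in hospital do not enter this risk set, and report their number by arm.

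The cost is close to nil. The change is to wording only. Length of stay and 30-day readmission are already taken from the medical record, and the discharge date is already needed to schedule the discharge questionnaires. No added visit, patient or instrument is required.

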#### **Table 3: Implementation Outcomes**

- c. Secondary patient-reported outcomes: Validated surveys that capture patient mood (HADS), engagement with care (PAM), and satisfaction with inpatient stay (HCAHPS, Net promoter score), outlined in Table 2 as well, will also be administered to intervention and control patients according through a pre-specified schedule.
- d. Sleep interruption and relationship to patient outcomes: Sleep interruptions between the control and intervention arms will be collected electronically from the hospital Electronic Medical Record

#### 3.10 Statistical Analysis Plan

Means with standard deviations, frequencies and percentages will be used to convey descriptive statistics. Standard tests of association (chi-squared, t-tests) will be used for comparing characteristics between the control and intervention arm. Inverse probability weighting using propensity scores modeled from baseline covariates and instrumental variable analysis will be the quasi-experimental approach used to minimize any confounding bias from our pseudorandomization process. We will model most outcomes with weighted multivariate generalized mixed effects regression models, focusing primarily on estimate the average treatment effect. The effect of unit will be modeled using a random intercept term. Care utilization outcomes will be compared using standard time-to-event models and log-rank testing. Final analyses will be performed when all data has been entered, cleaned, and locked.

All analyses will be based on an intent-to-treat framework. For missing covariate values, a multiple imputation approach will be used. Outcomes will be assumed to be missing at random; a sensitivity analysis will be conducted to assess the robustness of significant findings to different magnitudes of missing data mechanisms.

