#### 3.7 Patient Allocation to study groups

There is generally one patient per room and patient assignment to a room is largely driven by unit census (i.e., bed availability) as well as other clinical factors: e.g., need for an isolation room, nursing availability. All of these factors vary independently of the preferences of the patient or research team, reducing the risk for systematic bias. The unit of randomization is by pod on a floor. Research coordinators as part of the "on-boarding process" will also provide culturally competent instructions and in-person teaching for device use.

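### Within each service arm is the same thing as unit, so no planned method can separate a standing difference between paired units from the device effect; a pre-device contrast of the four units would help for the utilization outcomes

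*Combined protocol and SAP*

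**What the plan says.** Section 3.4 sets the arm by location. For colorectal patients on P10, "one side ('unit A') will be designated as an intervention arm while the other ('unit B') will serve as a control arm". On the Hospitalist service, "patients on ' unit G21' will be designated as the intervention arm, and patients admitted to 'unit G22' as the control arm". Section 3.7 states the principle: "The unit of randomization is by pod on a floor". There are thus four units, two per arm, and one per arm within each service.

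Section 3.4 defends this by saying of bed designation that "it is independent of the care delivery processes across the study floors / units". Section 3.7 adds that rooms are filled according to census and "other clinical factors: e.g., need for an isolation room, nursing availability", and argues that neither patients nor the research team influence these.

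Section 3.10 names the tools against confounding: "Inverse probability weighting using propensity scores modeled from baseline covariates and instrumental variable analysis". It says that these "will be the quasi-experimental approach used to minimize any confounding bias from our pseudorandomization process". It also gives unit a random intercept in the mixed models, and compares utilization outcomes by time-to-event models and log-rank tests without mentioning unit.

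The baseline variables listed in Section 3.8 are almost all patient characteristics, and none describes how a unit performed earlier. No section uses a pre-device period, a historical comparison or a negative control. Yet Section 3.8 takes length of stay and 30-day readmission from Epic, and Section 2.0 describes a phase before the device in the past tense: "Phase I of the PROSPER protocol involved the use of various standard of care methods".

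**The concern.** Haphazard bed assignment speaks to which patients land on which unit. It does not show that the two units of a pair would give equal outcomes if neither had the device. Units can differ in nursing practice, discharge habits, noise and layout. Every device patient in a service is on one unit and every control on the other, so any such difference is added to the estimated device effect.

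Shorter stay and fewer readmissions are named in the study hypothesis. A significant result on either could be a difference that existed before the device, and the plan contains nothing that would reveal it.

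**Working it through.** **1. The plan's own figure (Section 3.11).** Inputs: baseline mean 13, SD 5, 10% change, 250 per arm; two-sided alpha 0.05 is assumed because none is stated.
- Effect = 0.10 × 13 = 1.3 units. SE = 5 × √(2/250) = 0.447.
- Power = Φ(1.3/0.447 − 1.96) = 82.8%, which agrees with the stated minimum of 80%.
- The calculation treats patients as independent. The increase to 350 is attributed to reweighting and drop-out, not to differences between units.

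**2. What each planned method can do about a unit difference.**
- *Propensity weights.* Within a service, the probability of the device given the unit is 0 or 1, so unit cannot enter the propensity model; only patient covariates can. In a simulation with about 250 per arm and no device effect, weighting cut the bias from an imbalanced patient covariate from 0.45 to 0.00. It left an added unit offset almost untouched: 0.65 was estimated as 0.61, and 1.3 as 1.30.
- *Random intercept.* The arm contrast is a contrast of two unit means with two others, so it stays centred on device plus unit difference. Only its standard error can change. For EQ-5D at 350 per arm (175 per unit, equal units) and an assumed intraclass correlation of 0.01, the design effect is 1 + 174 × 0.01 = 2.74, and the SE goes from 0.378 to 0.378 × √2.74 = 0.626 units.
- *Instrumental variable.* No instrument is named. If it is bed or unit assignment, it is the arm itself and carries the same offset.
- *Log-rank and time-to-event models.* No unit term is stated.

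**3. Size of the consequence for utilization outcomes.** The documents give no unit difference, no SD of length of stay and no readmission rate for these units; all are assumed here. A patient-level normal test stands in for the planned comparison.
- False-positive probability = P(|Z + shift| > 1.96).
- Length of stay: shift = ln(1 + d) / (SD × √(2/n)). With SD 0.6 and n = 350 the denominator is 0.0454, so d = 5% gives 0.0488/0.0454 = 1.08 and d = 10% gives 0.0953/0.0454 = 2.10.
- Readmission at 20%: shift = d / √(2 × 0.2 × 0.8/350) = d/0.0302, so 3 points give 0.99 and 5 points give 1.65.
- If only one of two equal-sized pairs differs, the pooled shift halves.

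| Standing difference | Both pairs, same direction | One pair only |
|---|---|---|
| Length of stay 5% | 19% | 8% |
| Length of stay 10% | 56% | 18% |
| Readmission 3 points | 17% | 8% |
| Readmission 5 points | 38% | 13% |

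Equal and opposite differences in the two pairs cancel, leaving about 5%. At an effective 250 per arm, the both-pairs length-of-stay figures are 15% and 43%. At 350 with SD 0.4 they are 36% and 88%; with SD 0.8, 13% and 35%.

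**4. What a pre-device contrast would achieve.** In the same simulation with 250 pre-device patients per arm, subtracting the pre-device difference gave estimates within about 0.03 of zero and 4–5% rejections for offsets of 0, 0.65 and 1.3. The cost is precision: SE = SD × √(2/n_trial + 2/n_pre). For a 0.26 SD effect and 350 per arm in the trial, power is 68%, 80% or 87% with 350, 700 or 1,400 pre-device patients per arm, against 93% without the correction.

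**The case against.** The sponsor can reply that the study is openly pragmatic and quasi-experimental, that bed assignment is outside the team's control, and that unit is modelled. The first two are fair descriptions of the design, but they concern patient mix. The third is true of the mixed models, and the patient-level error rates above should not be read onto a model that honours the random intercept. It still does not move the estimate off the unit difference, and it is not stated for the log-rank comparisons.

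Three further objections stand and limit the point.
- *The larger error rates are a worst case.* They need both pairs to differ by the same amount in the same direction, with all 350 per arm fully informative, although Section 3.11 sets 350 to absorb reweighting variance and drop-out.
- *Availability of records is an inference.* A reader might infer that usable pre-device records for these four units are known to exist and were ignored. The documents do not say so. Section 3.8 speaks only of abstracting the record for the study, and Section 2.0 does not say where or when Phase I ran, or that a stable window followed it. Such records are likely, since these outcomes come from the routine record.
- *The remedy misses the primary outcome.* EQ-5D is collected by study survey and no pre-device values are described. The admission EQ-5D adjusts for patient mix, not for a unit effect that builds up during the stay.

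**Conclusion.** The point holds in a limited form. Arm and unit coincide within each service, and none of the methods in Section 3.10 can separate a standing unit difference from the device. A pre-existing difference in length of stay or readmission could therefore be credited to the device.

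Under the stated assumptions, moderate differences shared by both pairs raise the false-positive rate to 19–56% for length of stay and 17–38% for readmission. In one pair only, the ranges are 8–18% and 8–13%. These are illustrations, not estimates. A reader might infer that the paired units do differ, or that a positive result is probably false; the documents support neither. What they support is that the plan cannot tell. A pre-device contrast is a worthwhile addition for record-based outcomes, and a caution in wording is all it offers for EQ-5D.

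**What to change.** Add to Section 3.10, on condition that the record holds a stable window for all four units after PROSPER Phase I and before device go-live:

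1. Extract length of stay, ER visit and 30-day readmission, defined as in the trial, for eligible-type admissions in a fixed pre-device period (same diagnoses and services, at least 3 nights). Make the pre-period larger than the trial where possible.
2. Estimate intervention unit minus control unit, stratified by service, as a placebo check: on log length of stay, and as a risk difference for ER visit and readmission.
3. Report trial-period minus pre-period (difference-in-differences) on the same scales, as a sensitivity analysis beside each planned utilization result.
4. Word the EQ-5D conclusion as the effect of device plus unit.

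If no such window exists, say so and apply the wording in item 4 to the utilization results as well.

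The cost is one retrospective record pull, an IRB amendment and SAP text; enrolment, allocation and workflow do not change. The limits should be stated with the results. Parallel trends are assumed, so only a stable unit difference is removed. Consent and ability to complete surveys cannot be applied retrospectively, so selection at consent that differs by arm would not cancel. Precision falls as shown in the working. The primary outcome is not corrected.
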